## **8. STATISTICAL CONSIDERATIONS**

For full description of statistical considerations, please refer to the statistical analysis plan. A summary of the plan is described below. Unless otherwise indicated, all statistical tests will be 2 sided and tested at a significance level of 0.05. Corresponding 95% confidence intervals will be presented for statistical tests.

### **8.1 Study Endpoint Assessment**

#### **8.1.1 Primary Endpoint**

The primary endpoint is defined in Section 2.2.1. First, an Interval-Censoring Survival Analysis (ICSA) approach will be used to analyze the 48th month DBPCFC threshold data (Collett, 1993, Chapter 9, Taylor et al - 2009). Parametric (Log-normal, Weibull) and non-parametric dose-distribution model will be used to estimate the ED10 and the ED05, the doses predicted to provoke reactions in 10% and 5%, respectively, of the peanut-allergic population. Second, for each dose interval bounded by the NOAEL and LOAEL of the 48th month DBPCFC, we will conduct survival analysis with case-1 censoring (Huang – Wellner lecture notes, Kosorok et al, 1998) to estimate time to loss of desensitization.

Sample size was originally calculated for 80% power of detecting a p-value of 0.05 considering 2:1 placebo:peanut SLIT randomization and estimating a 50% pass rate for those randomized to placebo versus a 90% pass rate for those randomized to continue peanut SLIT . Adjusting for an estimated 10% drop out rate resulted in a minimum required sample size of 50 subjects. The sample size for the amended study has not been revised from the estimated minimum required size of 50 subjects since the study is in progress with an existing enrollment of 51 subjects. We intuitively think this number is adequate with the amended study design and analytical methods for the revised primary outcome of interest. However, to confirm our understanding, we plan on conducting simulations to study the power-sample size curve at 80% power based on study assumptions as discussed in the statistical methods section of the statistical analysis plan.

#### **8.1.2 Secondary Endpoints**

Secondary efficacy analyses will be based on the intention to treat (ITT) population only. Continuous endpoints will be analyzed using the Mixed Model Repeated Measures (MMRM) analysis. The mean changes from baseline will be analyzed using a restricted maximum likelihood (REML) based repeated measures approach. Analyses will include the fixed, categorical effects of population source, center and study week as well as the fixed covariates of baseline score and baseline score-by-study week interaction. An unstructured covariance structure will be used to model the within-patient errors. If this analysis fails to converge, the following structures will be tested: first order ante dependence, heterogeneous first order autoregressive, heterogeneous compound symmetry and compound symmetry. The covariance structure converging to the best fit, as determined by Akaike's information criterion, will be used in the analysis (Mallinckrodt et al,

2008). The Kenward-Roger approximation will be used to estimate the denominator degrees of freedom.

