**Protocol Approval**

## Synopsis

Title	Peanut Sublingual Immunotherapy and Induction of Clinical Tolerance in Peanut Allergic Children (TLC)
Short Title	Peanut SLIT and Tolerance
Clinical Phase	Phase I/II – Safety and Efficacy
IND	14326
Sponsor	A. [name]
Principal Investigator	A. [name]
Participating Site	University of North Carolina at Chapel Hill (after March 26, 2012) Prior to March 26, 2012: Duke University Medical Center, Durham, NC
Accrual Objective	55 subjects to allow for 45 subjects to complete study interventions
Study Design	A prospective, randomized open-label study to assess the induction of desensitization after at least 48 months of peanut sublingual immunotherapy (SLIT) and the persistence of desensitization (sustained unresponsiveness) following a period of up to 17 weeks of peanut avoidance.
Study Duration	Up to 66 months per subject; Duration varies dependent upon subject’s randomized period of study drug withholding.
Primary Endpoints	
 
• An estimate of the population sensitization threshold as assessed by the 48th month DBPCFC, predicted to provoke reactions in 5% and 10% of the peanut-allergic population.
 
• Multiplicative or differential change in the population sensitization threshold as assessed by the 48th month DBPCFC with a unit change in covariates.
 
• An estimate of time to loss of desensitization for the following events:             
 
- Subject's true sensitivity threshold to reduce by half.
 
- Subject's true sensitivity threshold to maintain at the same level of LOAEL.
 
- Subject's true sensitivity threshold to drop by at least one level of LOAEL.
 
- Subject's true sensitivity threshold to remain at or above MCRT.
 
 
 
• Estimates of the proportion of patients at a fixed time for any of the above events that define loss of desensitization.
 
• Multiplicative change in hazard of loss of desensitization with a unit change in covariates.
 

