### **5.2 Enrollment**

Up to 55 children may be enrolled in this protocol, including the participant allowed under an exception to enroll from the CoFAR 4 Pro0003579 (not counted in the data analysis for this study). Accounting for a 10% drop out rate, we anticipate having approximately 45 children eligible for randomization during the blinded phase of the study.

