***Build-up and Maintenance for Crossover Subjects from CoFAR 4 Protocol***

Subjects completing the Sublingual Immunotherapy for Peanut Allergy: A Randomized, Double-Blind, Placebo-Controlled, Phase I/II Pilot Study with Whole Peanut Extract (Duke IRB Pro0003579, UNC IRB 11-2301, CoFAR4) who do not pass the 164 week 10 gm DBPCFC may enroll in this Peanut SLIT and Tolerance study. These subjects will have completed 3 years of 1386 mcg peanut SLIT maintenance. Upon completion of the CoFAR 4 study Pro0003579 10 gm DBPCFC, subjects may resume an escalation schedule starting with the 2000 mcg dose in this SLIT (11-2308, TLC) protocol. The first dose will be an observed dose the day following the CoFAR4 10gm DBPCFC (study visit\*). The 3000 mcg escalation may be done at home if the subject did not experience symptoms (other than oral pruritis). The final 4000 mcg dose escalation will be an observed dose in the clinical research unit(study visit \*). The subjects will then follow the schedule of Peanut SLIT and Tolerance in this protocol (11-2308) including the endpoint DBPCFCs.

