4. OVERALL STUDY DESIGN AND PLAN

This is a Phase 2, open label 52-month study designed to evaluate the safety and efficacy of peanut SLIT in inducing clinical desensitization among peanut allergic children.

The study consists of a Screening visit, a Baseline Visit (sometimes combined with the Screening Visit), a build-up phase (approximately, 20 weeks), a Maintenance phase (42 months) and finally, a Sustained Unresponsiveness phase (17 weeks). The total duration of the study, including Screening and the follow-up period, is approximately 225 weeks. We note that all the 24 subjects that have passed the 48 month time point and have been waiting to be administered the 48th month DBPCFC are continuing to dose daily. Because, based on prior evidence, the benefit of continued dosing past 48 months is considered to be negligible on the overall treatment outcome, a slight extension of maintenance phase is considered negligible for such subject.

Following the qualifying entry 1000 mg peanut protein DBPCFC administered at the baseline, subjects will be administered diluted pumps of concentrated peanut protein extract (5000 mcg/ml) based on the build-up dosing scheme to reach an escalated dose of 4000 mcg. Visits for build-up doses will occur prior to changing peanut dilutions or every 4 weeks. Subjects completing the Duke IRB Pro0003579, UNC IRB 11-2301, CoFAR4 who do not pass the 164 week 10 gm DBPCFC may enroll in this study and resume an escalation schedule starting with the 2000 mcg dose in this SLIT (11-2308, TLC) protocol. This defines the build-up phase.

After completing the escalation schedule, subjects will continue to be administered 4000 mcg of peanut SLIT daily at home and will return to the clinical research unit for follow-up visits every 6 months or more frequently for new or significant symptoms. This defines the maintenance phase.

At the 48th month visit, all subjects undergo a 5000 mg peanut protein DBPCFC to verify desensitization, defined as a reaction threshold greater than MCRT (300 mg of peanut protein). At the same visit, subjects are randomized to one of the 17 weeks of SU phase for administration

of the final DBPCFC to assess SU. SU is claimed if the final DBPCFC reaction threshold is greater than or equal to the larger of MCRT and the 48th month DBPCFC sensitivity threshold. Subjects who fail the 48th month DBPCFC, hence not desensitized, will not be administered the final challenge.

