10.2 Secondary & Exploratory Efficacy Analysis

Secondary efficacy analyses will be based on the ITT population only. Continuous endpoints will be analyzed using the MMRM analysis. The mean changes from baseline will be analyzed using a restricted maximum likelihood (REML) based repeated measures approach. Analyses will include the fixed, categorical effects of population source, center and study week as well as the fixed covariates of baseline score and baseline score-by-study week interaction. An unstructured covariance structure will be used to model the within-patient errors. If this analysis fails to converge, the following structures will be tested: first order ante dependence, heterogeneous first order autoregressive, heterogeneous compound symmetry and compound symmetry. The covariance structure converging to the best fit, as determined by Akaike's information criterion, will be used in the analysis (Mallinckrodt et al, 2008). The Kenward-Roger approximation will be used to estimate the denominator degrees of freedom. Significance test will be based on least-squares means using a two-sided $\alpha=0.05$ test and two-sided 95% confidence intervals will be presented. The comparison of interest is the contrast between the weeks of challenges and baseline.

[figure not shown]
MMRM analysis will be implemented with a modified baseline observation carried forward (BOCF)/last observation carried forward (LOCF) algorithm. Where the study medication was discontinued due to lack of efficacy or to an AE or the cause is unknown, the baseline value is used for all values after the last date that study medication was taken (as shown in the Daily Diary). If the study medication was discontinued for any other reason, then the last observation will be carried forward. This is an MNAR analysis that investigates changes in endpoints using logical assumptions. Assessment values collected after treatment discontinuation, and true missing values (after withdrawal from the study) will be imputed in this manner.

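### Population source in the MMRM is either an empty factor or, if the CoFAR 4 child is analysed with equal-margin LS means, it gives that child half of each stand-alone change from baseline

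*Protocol*

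**What the plan says.** Protocol 8.1.2 and SAP 10.2 specify the same mixed model for change from baseline in the continuous secondary endpoints: "Analyses will include the fixed, categorical effects of population source, center and study week", plus baseline and baseline-by-week. There is no source-by-week term. SAP 10.2 adds "Significance test will be based on least-squares means" and "The comparison of interest is the contrast between the weeks of challenges and baseline". Neither document defines the levels of population source or center, or says whether LS means use equal or observed margins.

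On the crossover route:
- Protocol 5.2 counts enrollment as "including the participant allowed under an exception to enroll from the CoFAR 4 Pro0003579 (not counted in the data analysis for this study").
- Protocol 5.5, on crossover subjects, says: "These subjects will have completed 3 years of 1386 mcg peanut SLIT maintenance". It then places them on this trial's schedule, including the endpoint challenges.
- SAP section 4 says that CoFAR 4 subjects "who do not pass the 164 week 10 gm DBPCFC may enroll in this study" and mentions no exclusion from analysis.
- SAP section 7 defines ITT as all patients randomized, with no exception, and SAP 10.2 runs the secondary analyses on ITT only.

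On center, the Synopsis lists one site at a time: "University of North Carolina at Chapel Hill (after March 26, 2012"), with Duke before that date.

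**The concern.** An LS mean conventionally averages the levels of a fixed factor with equal weight, whatever the head count. The outcome is already change from baseline, so a test of a challenge week against baseline is a test of the LS mean itself. An additive source effect does not cancel from it. If one level holds a single child, that child's data supply half of the tested quantity.

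This child would also be atypical. SAP 8.1 takes baseline as the last value before the first dose of study drug, which for a CoFAR 4 child follows three years of peanut SLIT. The child's change from baseline therefore measures something different from the other children's. At stake are the precision and meaning of the stand-alone changes in peanut-specific IgE and IgG4, skin test size and basophil reactivity.

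**Working it through.** **Plan's own figure.** The documents give no LS-mean weight or standard error (SE) to reproduce. The sample size behind n = 45 does reproduce: 90% versus 50%, 2:1, two-sided 0.05 and 80% power give 15 + 30 = 45, and 45/0.9 = 50, as in Protocol 8.1.1. Protocol 5.2 also expects about 45 children to reach randomization.

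**Inputs**
- n = 45 children analysed (Protocol 5.2).
- k = children in the CoFAR 4 level; k = 1 from the singular wording of Protocol 5.2.
- m = 5 post-baseline visits (months 12, 24, 36, 48 and the final challenge; Protocol Appendix 1), or 4 without the final one.
- rho = within-child correlation of changes, compound symmetry. The documents give none; 0 to 0.8 is assumed.
- SD of a single change = 1. LS-mean margins equal (assumed).

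**Case A: Protocol 5.2 governs.** The child is out, and source has one level and drops out. The child's weight is 0 and the SE ratio is 1.00.

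**Case B: the child is analysed.** The equal-margin LS mean at week t is the raw week mean plus (0.5 − k/n) × (estimated source effect). The source effect is a between-child contrast and is uncorrelated with the raw week mean, so:

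Var = 1/n + (0.5 − k/n)² × (1/k + 1/(n − k)) × V, with V = [1 + (m − 1) rho]/m.

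*Weight.* For k = 1 the child's total weight is 1/n + (0.5 − 1/n) = 0.50, whatever n or rho. With observed margins it is 1/45 = 0.022.

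*SE ratio.* For k = 1, dividing by the SE without the factor gives √(1 + V(n − 2)²/[4(n − 1)]). At n = 45, 43²/(4 × 44) = 10.506. The reference SE is √(1/45) = 0.149.

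| m | rho | V | SE (SD units) | Ratio |
|---|---|---|---|---|
| 5 | 0 | 0.20 | 0.263 | 1.76 |
| 5 | 0.3 | 0.44 | 0.353 | 2.37 |
| 5 | 0.5 | 0.60 | 0.403 | 2.70 |
| 5 | 0.8 | 0.84 | 0.467 | 3.13 |
| 4 | 0.8 | 0.85 | 0.470 | 3.15 |

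**Sensitivity**
- Adding baseline and baseline-by-week moves the rho = 0.5 ratio only from 2.70 to 2.71.
- A first-order autoregressive structure gives 2.08 (rho 0.3) to 3.11 (rho 0.9).
- Over n = 24 to 51 and rho = 0 to 0.9 (m = 5), the ratio runs from 1.43 to 3.47.
- With 2, 3 or 5 crossover children (n = 45, m = 5, rho = 0.5), it is 1.98, 1.68 or 1.39.
- Observed margins return 0.149, a ratio of 1.00.

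**Contrasts that escape.** The source term is identical at every week, so it cancels from a difference between two weeks. It also cancels from a desensitized-versus-failed difference.

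**Center.** No center sizes are given. SAP section 1 has 24 of 51 enrollees past 48 months, and Protocol 5.8 refers to such a group as of 22 February 2016. Counting back 48 months gives February 2012, just before the move from Duke. A 24/27 split by enrollment site would give at most √(1 + 51 × (0.5 − 24/51)² × (1/24 + 1/27)) = √1.0035 = 1.00. The SAP count is undated, so this is only indicative.

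**The case against.** The strongest objection is that the one sentence from which the single crossover child is known also says that the child is not analysed. On that text there is no half weight and no loss of precision. The redundant factor falls out of the fit, and removing it is tidying. This stands, and it means that the inflation cannot be stated as what the plan will produce. It does not settle the matter: the SAP's ITT definition, which a programmer would follow, has no such exclusion. SAP 9.2 lets a data review before database lock remove patients for protocol deviations, but an approved enrollment exception is not plainly a deviation.

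Other limits also stand. The source levels and equal margins are inferred. The child enters ITT only if randomized after the 48-month challenge, which the documents do not establish. Protocol 5.5 and SAP section 4 speak of crossover subjects in the plural, and more of them would shrink the effect.

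A reader might go further and infer that one child will dominate every reported immune result, that center does the same damage, or that real immune changes will be missed. The documents do not support this. The stated secondary endpoint compares desensitized with failed children, where the term cancels. Nothing shows a badly unbalanced center. No expected size is given for any immune change, so no loss of power can be fixed.

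**Conclusion.** The point holds in conditional form. Population source has no useful role in this model: it is empty under Protocol 5.2 and potentially harmful under the SAP's ITT definition, and the two documents do not agree on which applies.

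The harm needs four conditions together: the child is analysed, has been randomized, is alone in the level, and LS means use equal margins. Given these, the half weight is exact. The rise in standard error is about 1.8-fold to 3.2-fold at n = 45 for an assumed correlation of 0 to 0.8. It is confined to stand-alone LS-mean changes from baseline, which is the comparison that SAP 10.2 names. For center, the finding is only that the term is undefined. This is a secondary analysis, so the primary threshold and time-to-loss analyses are untouched.

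**What to change.** 1. Delete population source from the mixed model in Protocol 8.1.2 and SAP 10.2, keeping study week, baseline and baseline-by-week.
2. State in the ITT definition in SAP section 7 that the CoFAR 4 participant is not analysed, so that it agrees with Protocol 5.2.
3. If population source or center is kept, define its levels and specify LS means with observed-margin (head-count) weights.

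The cost is one line in the Protocol and two in the SAP, with the usual IRB approval of an amendment. No data, visits or patients are affected.

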## **8.2 Subject and Demographic Data**

### **8.2.1 Baseline Characteristics and Demographics**

Summary descriptive statistics for baseline and demographic characteristics will be provided for all enrolled participants. Demographic data will include age, race, sex, body weight, and height; these data will be presented in the following manner:

1. Continuous data (i.e., age, body weight, and height) will be summarized descriptively by mean, standard deviation, median, and range.
2. Categorical data (i.e., sex and race) will be presented as enumerations and percentages.

Statistical presentation for baseline and demographic characteristics may be further summarized by study drug group and baseline peanut-specific serum IgE. Statistical comparison of these groups will be performed as summarized above.

### **8.2.2 Study Completion**

The percentage of participants who complete the study, losses to follow-up, times to lost to follow-up, and reasons for discontinuation (e.g., adverse events) will be presented. Statistical presentation of study completion will be further presented via analysis of the secondary endpoints summarized.

## **8.3 Interim Analyses to Ensure Safety**

All adverse event reports will be reviewed by the DSMB in its convened meetings. The annual summary of all adverse events and any audit reports will be reviewed annually by the DSMB.

## **9. IDENTIFICATION AND ACCESS TO SOURCE DATA**

### **9.1 Data Management**

All records generated during the visits will be stored in the Food Allergy database, on the immunology server, and in the individual subject's research study binder. The subject's information is accessible only to the investigator and his designated colleagues.

### **9.2 Access to Data**

The subject's information is accessible only to the investigator or his designated colleagues by individual password or direct viewing of the research record. The research records will be kept locked in the investigator's research area. The investigator is required by law (21CFR312.62) to keep accurate case records until two years after the IND is marketable or three years after the investigation is discontinued (whichever is longer). Any information placed in the medical record will remain in the medical record indefinitely.

## **10. QUALITY CONTROL AND QUALITY ASSURANCE**

The sponsor/investigator is required to keep accurate records to ensure that the conduct of the study is fully documented. The sponsor/investigator is responsible for regularly reviewing the conduct of the trial, for verifying adherence to the protocol, and for confirming the completeness, consistency, and accuracy of all documented data.

### **10.1 Data Handling**

The investigator is required to ensure that all CRFs are legibly completed for every participant entered in the trial.

## **11. ETHICAL CONSIDERATIONS AND COMPLIANCE WITH GOOD CLINICAL PRACTICE**

### **11.1 Statement of Compliance**

This study will be conducted using good clinical practice (GCP), as delineated in *Guidance for Industry: E6 Good Clinical Practice Consolidated Guidance*, and according to the criteria specified in this study protocol. Before study initiation, the protocol and the consent documents will be reviewed and approved by an appropriate IRB. Any amendments to the protocol or to the consent materials must also be approved before they are implemented.

### **11.2 Consent and Assent Process**

The consent process is a means of providing information about the study to a prospective participant and/or to the parent/guardian. The consent process allows for an informed decision about participation in the study. The participant or the parents/legal guardians will be asked to read, sign, and date a consent form before entering the study, undergoing any screening procedures (e.g., physical exam, food challenge, skin testing), taking study drug, or undergoing any study-specific procedures. Minors will sign assent as appropriate. The consent form will be revised whenever the protocol is amended with a study design change. A signed copy of the consent will be given to a prospective participant and/or parent/guardian for review. The prospective subject and parent/guardian are told that being in the study is voluntary and that he or she may withdraw from the study at any time, for any reason.

[figure not shown]
### **11.3 Privacy and Confidentiality**

A participant's privacy and confidentiality will be respected throughout the study. Each participant will be assigned a sequential identification number and these numbers will be used to collect, store, and report participant information.

## **12. RESOURCE SHARING**

Subject information will only be shared using the subject study identification number. All other identifiers of the subject will be removed prior to the release of information. If the results of the trial are published the study number may be used; participants' names will not be included in publications.

